#### *16.3 Describe any procedures that will be used for quality control of collected data.*

**Response:** See above description of data management. In addition, we will follow procedures used in our lab previously for the assurance of quality online data. Specifically, we will review completion times and response patterns. Extremely brief (i.e., less than ½ of estimated) completion times for online surveys, or seemingly random response patterns (e.g., inconsistent or uniform responding) will prompt a reminder email to participants regarding study expectations.

### **17.0 Confidentiality**

#### **A. Confidentiality of Study Data**

*Describe the local procedures for maintenance of confidentiality of study data and any records that will be reviewed for data collection.*

*17.1 A. Where and how will all data and records be stored? Include information about: password protection, encryption, physical controls, authorization of access, and separation of identifiers and data, as applicable. Include physical (e.g. paper) and electronic files.*

**Response:** For in-person interview and self-report assessments, data will be stored on a computer in the UB Alcohol Research Lab, and backed-up regularly. The computer itself is password protected, and the lab in which the computer is kept is locked. For online (electronic) data, detailed procedures for protecting electronic data include the creation of random ID numbers which are later hooked into a “hash ID”. Thus, at no point are identifying information and participant data linked in cyberspace. We will further safeguard against breaches of confidentiality by coding participant data by ID number rather than by name and by keeping information linking these ID numbers to specific individuals in separate files (i.e., identifying information is stored in a separate electronic file with a separate password, accessible only to project staff). Further, no individuals will be identified by name nor will any identifying information be offered when presenting data in lectures, seminars, professional presentations, or papers. Additionally, as we have done in the past, we will obtain a certificate of confidentiality from NIH in order to enhance the protection of the data, and to minimize concerns about reporting on illegal drug use.

**17.2 A. How long will the data be stored?**

Response: Five years.

**17.3 A. Who will have access to the data?**

Response: Only study staff will have access to the data. At a later date, others may access the data for secondary data analysis. However, at this point, the data will be deidentified.

**17.4 A. Who is responsible for receipt or transmission of the data?**

Response: Drs. [name] and [name] are primarily responsible for the receipt and transmission of the data. Staff personnel such as the graduate student and the project manager will also be involved in this task.

**17.5 A. How will the data be transported?**

Response: Electronically, via the internet. Please see description above.

**B. Confidentiality of Study Specimens**

*Describe the local procedures for maintenance of confidentiality of study specimens.*

- N/A:** No specimens will be collected or analyzed in this research.  
(Skip to Section 19.0)

**18.0 Provisions to Monitor the Data to Ensure the Safety of Subjects**

**18.1 Describe the plan to periodically evaluate the data collected regarding both harms and benefits to determine whether subjects remain safe.**

Response. For in-person assessments, all study staff, including interventionists and research assistants, will be trained to identify serious adverse events that may be subject to mandatory reporting guidelines. Related to this, staff also will be trained to identify any events that, though falling short of mandatory reporting requirements, may nonetheless warrant immediate clinical attention (e.g., recent sexual assault or assault-related distress, severe negative alcohol consequences). Any evidence that a participant may be in immediate and identifiable danger, or is experiencing other significant and acute distress (e.g., recent assault) will trigger an “emergency procedures” protocol (see description below). follow up interviews will have specific measures and interview questions that will serve as “flags” for our interventionists to assess for signs of distress. In cases where distress is indicated, interventionists and follow-up interviewers will have a protocol as to specific follow-up questions, and a link to referral resources. Finally, as we have done in previous work, our online assessments will have a “**REQUEST for CONTACT**” button. Participants are instructed to click on this button if they are distressed and would like to talk to a member of the project staff. Clicking this will generate an e-mail to our staff, and [name] (UB), who is a clinical psychologist, will contact the participant within 24 hours. These procedures are described in greater detail, below.

*Describe what data are reviewed, including safety data, untoward events, and efficacy data.*

Response: Please see response above.

**18.2 Describe any safety endpoints.**

Response: As described above, safety endpoints involve identified distress or danger to a participant. It is important to note that our procedures are designed to balance reasonable measures to maintain participant safety, while at the same time not discouraging accurate and truthful reporting on the part of participants. As described above, policies such as those involving the implementation of Title IX have been developed with this specific challenge in mind. Wanton reporting of every distressing event has

the potential not only to have a deleterious effect on the study, but also can be iatrogenic for the participants themselves.

*18.3 Describe how the safety information will be collected (e.g., with case report forms, at study visits, by telephone calls with participants).*

Response: See above.

*18.4 Describe the frequency of safety data collection.*

Response: As is outlined in the description of our study approach above, we will collect data pre- and post-intervention, and then at follow-ups. Data will be reviewed for safety concerns at each data collection occasion.

*18.5 Describe who will review the safety data.*

Response: Drs. [name] and [name] and associated project staff (project manager, graduate student) will review the safety data. Requests for contact will come to [name], and she will oversee these procedures.

*18.6 Describe the frequency or periodicity of review of cumulative safety data.*

Response: Safety reviews will be ongoing throughout the course of the study. Please see descriptions above.

*18.7 Describe the statistical tests for analyzing the safety data to determine whether harm is occurring.*

Response: There are no statistical tests to determine safety.

*18.8 Describe any conditions that trigger an immediate suspension of the research.*

Response: The research would be suspended if, in the highly, highly unlikely event, it was determined that the research was leading to immediate and identifiable distress or danger to participants.

## **19.0 Withdrawal of Subjects**

*19.1 Describe anticipated circumstances under which subjects may be withdrawn from the research without their consent.*

Response: A participant could be withdrawn without his or her consent in the event that it was determined that s/he was doing something purposefully to undermine the project. Such circumstances are hard to imagine, but might include mistreating project staff or other participants. This is not expected, both because such behavior is very unusual in study participants, and in 15 years of acting as the PI of the Alcohol Research Lab, [name] has never encountered an event so serious that it would call for termination of research participation. Still, it is possible, however unlikely.

*19.2 Describe any procedures for orderly termination.*

Response: Participants would first be contacted about the event, and efforts to resolve the problem would be made. The goal would always be to keep the participant enrolled in the study. If it were determined that this was not possible, the participant would be told of her or his removal, and compensated for any time that he/she had already put into the study. No future compensation would be offered, and no further contact would be initiated by study staff.

*19.3 Describe procedures that will be followed when subjects withdraw from the research, including retention of already collected data, and partial withdrawal from procedures with continued data collection, as applicable.*

**Response:** Participants can withdraw from the study at any time. If a participant withdraws, no efforts at future contact (e.g., follow-up assessments) would be initiated by the project staff.

## 20.0 Risks to Subjects

### 20.1 List the reasonably foreseeable risks, discomforts, hazards, or inconveniences to the subjects related to their participation in the research.

**Response:** Risks posed to participants in the present study are minimal. Evidence shows that assessments of sexual assault and related experiences may be conducted without serious deleterious psychological effects. Some participants may experience minor emotional discomfort or embarrassment in responding to questions pertaining to potentially sensitive topics such sex or sexual assault, or even substance use. This could occur during completion of self-report assessments, or during individual interviews. However, such discomfort is relatively rare, and is almost always mild and transient. Our labs have been conducting both in-person and online assessments of these phenomena for more than a decade and are well equipped to manage participant needs in the event that distress occurs (see below).

As this dyad-based intervention focuses on motivating a sense of agency for action, through enhancement of personal responsibility and relationship between friends, another potential risk pertains to inadvertent, iatrogenic effects of the intervention. For example, in cases where sexual victimization occurs to one of the dyad members – or even if it doesn't- the other member of the dyad may believe that somehow she is to blame. We plan to assess such effects carefully, with an eye toward both (1) modification of the intervention to decrease such iatrogenic effects, and also (2) ensuring the wellness of the participants enrolled in our study. Efforts to address the first of these issues (future intervention modification) are described in the body of the proposal. To address specific participant wellness concerns, here we outline several steps that we will take in the "Adequacy of Protection Against Risk" section, below.

Lastly, because our study focuses on high-risk (i.e., heavy drinking) women, it is possible and perhaps even likely that women will experience some kind of event that falls along the spectrum of assault behaviors during the course of follow-up. Though this assault would not be as a result of the intervention itself, it is a risk that our participants could incur during the period of follow-up and as such, is something that we have planned to address in our procedures. These procedures are described below.

### 20.2 Describe procedures performed to lessen the probability or magnitude of risks, including procedures being performed to monitor subjects for safety.

**Response:** In an effort to prevent or minimize discomfort or embarrassment in responding to questions we will reiterate our procedures for protecting participant confidentiality in on-line questionnaires. Additionally, as a precautionary measure, all web surveys will be accompanied by a treatment referral list, as well as by contact information for study clinical staff in the event that they become distressed by reporting on traumatic events and would like to speak further with a mental health professional. Detailed procedures for protecting electronic data are described within the body of this proposal, and include the creation of random ID numbers which are later hooked into a "hash ID". Thus, at no point are identifying information and participant data linked in cyberspace. We will further safeguard against breaches of confidentiality by coding participant data by ID number rather than by name and by keeping information linking these ID numbers to specific individuals in separate files (i.e., identifying information is stored in a separate electronic file with a separate password, accessible only to project staff). Further, no individuals will be identified by name nor will any identifying information be offered when presenting data in lectures, seminars, professional presentations, or papers. Additionally, as we have done in the past, we will obtain a certificate of confidentiality from NIH in order to enhance the protection of the data, and to minimize concerns about reporting on illegal drug use.

First, as part of the intervention, we will explicitly discuss the ways in which a sense of responsibility to someone, is different from a sense of responsibility for someone, and that though there are ways in which friends may help one another to decrease sexual assault risk, this does not mean that they alone are responsible for one another'. Second, all participants will receive as part of the general study debriefing procedure, a description of possible iatrogenic intervention effects, including

guilt and blame. Participants will be encouraged to discuss these concerns with interventionists at follow-up, with one of the two PIs, or to seek out additional support, available through our referral list. Third, as follow up interviews now have specific measures and interview questions that will serve as “flags” for our interventionists to assess for signs of distress. In cases where distress is indicated, interventionists and follow-up interviewers will have a protocol as to specific follow-up questions, and a link to referral resources. Finally, as we have done in previous work, our online assessments will have a “**REQUEST for CONTACT**” button. Participants are instructed to click on this button if they are distressed and would like to talk to a member of the project staff. Clicking this will generate an e-mail to our staff, and [name] (UB), who is a clinical psychologist, will contact the participant within two business days.

*Assessment and Management of Adverse Events.* Our procedures for managing adverse events are informed by the collective experience of our team in conducting research with women at risk for assault and other adverse, alcohol-related outcomes, including [name] training as a Clinical Psychologist and her experience as the Director of the Clinical Psychology program, including the Psychological Services Clinic. All study staff, including interventionists and research assistants, will be trained to identify serious adverse events that may be subject to mandatory reporting guidelines. Related to this, staff also will be trained to identify any events that, though falling short of mandatory reporting requirements, may nonetheless be warranting immediate clinical attention (e.g., recent sexual assault or assault-related distress). Any evidence that a participant may be in immediate and identifiable danger, or is experiencing other significant and acute distress (e.g., recent assault) will trigger an “emergency procedures” protocol. In these cases, the PI ([name]) will be notified by telephone and text of such an event. In cases where this “triggering” occurs via online assessment, [name] will make immediate phone contact with the participant to further evaluate safety and other concerns. In cases where the triggering takes place during in-person assessments, [name] will be contacted and will speak with the participant either by phone (if [name] is off-site) or in person to provide further assessment and to formulate an action plan to ensure the participants safety and wellbeing. In the unlikely event that [name] cannot be reached within the hour, either the Campus Psychological Services Center (PSC) or if outside of business hours, Campus Security will be contacted. In cases where the threat is determined not to be imminent, [name] will work with the participants to connect them to services at either the PSC or the university-based Counseling Center. At both of these facilities, students may receive either free or reduced rate services. Drs. [name], [name], and [name] have close ties to these facilities. This will ensure a seamless pathway of care.

*Application of Title IX Reporting.* In addition, we have carefully reviewed reporting requirements for Title IX, consulted with our UB Title IX representative ([name], Director of Equity, Diversity, & Inclusion (EDI); <https://www.buffalo.edu/equity/obtaining-assistance/sex-discrimination-and-sexual-harassment/title-ix.html>), and read a number of opinions and discussions regarding responsible adherence to these requirements as they pertain to campus life, and how they may pertain to research (e.g., <http://www.chronicle.com/article/Mandatory-Reporting-for-Title/141785>; <https://www2.ed.gov/about/offices/list/ocr/docs/qa-201404-title-ix.pdf>; ). Based on these investigations, it appears that, because mandatory reporting among researchers may act as a deterrent to research participation and thus may interfere with understanding of the very problem that such research is intended to address

[https://cola.unh.edu/sites/cola.unh.edu/files/departments/Prevention%20Innovations%20Research%20Center/pdf/Prevention\\_Innovations\\_Research\\_Center\\_Title\\_IX\\_Human\\_Subject\\_Research\\_White\\_Paper\\_Nov\\_5\\_2015docx.pdf](https://cola.unh.edu/sites/cola.unh.edu/files/departments/Prevention%20Innovations%20Research%20Center/pdf/Prevention_Innovations_Research_Center_Title_IX_Human_Subject_Research_White_Paper_Nov_5_2015docx.pdf)), the reporting of assault events that may occur in the context of research such as the proposed project would not meet the standard of mandatory reporting as outlined by Title IX (Note that our research still would be subject to other mandatory reporting demands, as described above). Still, guidelines around Title IX adherence change with time, and as such, we will continue to work closely with our Title IX officer to arrive at procedures that maintain the rights, confidentiality, and protections of our participants, while still complying with reporting laws.

Further, because “Best Practices” of Title IX procedures facilitate understanding on the part of students as to who may or may not be a mandated reporter, we will include in our informed consent a description of Title IX and its parameters. We will explicitly note that research reporting does not fall under mandated reporting guidelines, and will provide information for how to get in contact with the EDI offices for further information and guidance about reporting and assistance.

20.3 *If applicable, indicate which procedures may have risks to the subjects that are currently unforeseeable.*

Response: To our knowledge, there are no procedures which may have risks that are unforeseeable.

20.4 *If applicable, indicate which research procedures may have risks to an embryo or fetus should the subject be or become pregnant.*

Response: Our research procedures carry no risks for an embryo or fetus.

20.5 *If applicable, describe risks to others who are not subjects.*

Response: To our knowledge, there are no risks associated with our study procedures to others who are not research subjects.

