### Screening, Eligibility, and Recruitment (All Stages)

Because women who drink heavily are at greatest risk for SA, we will recruit heavy drinking (i.e. 4 or more drinks in a single sitting [HED] 2 or more times monthly in past 3 months) women into our sample. These women will be recruited via campus and community-wide advertisements for a study of "women's social experiences". Telephone screens will be used to determine eligibility. For Stages 2 and 3, friend dyads will be recruited. Both women in the dyad must meet HED criteria. Additional eligibility criteria will be that each individual in the dyad reports going out (not necessarily drinking) together  $\geq$  1/week, and identifies the other dyad member a close friend. Eligible participants will be scheduled for a focus group session (for Stage 1) or for an initial intervention assessment session (for Stages 2, 3). Women must be college students, but can be from any of the greater Buffalo area's nine colleges. Thus, development will not be based on a single campus.

**Recruitment Considerations:** All kinds of friends could be valuable in helping to prevent SA. In the proposed study, we focus on female dyads with 2 heavy drinking members. We have chosen these dyad characteristics in this early phase of development for several reasons.

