### **Setting**

**11.4** *Describe all facilities/sites where you will be conducting research procedures. Include a description of the security and privacy of the facilities (e.g. locked facility, limited access, privacy barriers). Facility, department, and type of room are relevant.*

Response: Data collection will be conducted via in person interviews and online. For online assessments, assessments will be completed by participants in their own local setting. Instructions for the online surveys will suggest to participants that they complete online surveys at a time and in a place where privacy can be ensured. In person assessments will be conducted on UB's North Campus, in [name] research lab.

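### For emergencies identified remotely, the only staff backup in section 20.2 when the clinician cannot be reached is a campus service, which may not be able to get help to a woman off campus

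*Combined protocol and SAP*

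**What the plan says.** The emergency pathway is in section 20.2, under Assessment and Management of Adverse Events. Section 18.1 mentions the same pathway and points forward to it: "protocol (see description below".

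- **Trigger.** "Any evidence that a participant may be in immediate and identifiable danger", "or is experiencing other significant and acute distress (e.g., recent assault"). Online and in-person assessments are both covered.
- **First response.** The principal investigator is notified by telephone and text. For an online trigger, the clinician phones the woman at once. For an in-person trigger, the clinician speaks with her by phone or face to face. (Names are removed from the public text, so I write simply of the clinician.)
- **Backup.** If the clinician has not been reached within an hour, "either the Campus Psychological Services Center (PSC) or if outside of business hours, Campus Security will be contacted".
- **Threat judged not imminent.** The clinician works with the woman to "connect them to services at either the PSC or the university-based Counseling Center".

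Sections 18.1 and 20.2 also give interventionists and follow-up interviewers a set of follow-up questions and a link to referral resources when distress is indicated. Section 13.3 says that the referral list accompanying the surveys holds local and national resources.

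**The concern.** The backup is tied to one campus, while much of the follow-up takes place away from it. Under Screening, Eligibility, and Recruitment, women "can be from any of the greater Buffalo area's nine colleges"; section 5.3 puts the number at close to twelve. Section 11.4 says that online "assessments will be completed by participants in their own local setting", and advises women to "complete online surveys at a time and in a place where privacy can be ensured". Section 25.6 accepts that a woman may be out of state when she answers.

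Staff who follow 20.2 to the letter for such a woman, with the clinician unreachable in the evening, would call Campus Security. That body may be unable to get help to her, and up to an hour would already have passed. Section 20.1 accepts that an assault-type event during follow-up may well happen, and 20.2 gives a recent assault as its example of a trigger. The trigger is therefore foreseeable, even if this chain of events is not common.

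**Working it through.** The plan gives no figure to reproduce. The check is whether the stated backup fits each kind of contact at which an emergency could come to light.

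| Contact | Where the woman is | Does the campus backup fit? |
|---|---|---|
| In-person assessment (section 11.4) | UB North Campus | Yes |
| Bi-weekly online survey over 12 weeks (Stage 3 Procedures) | Wherever she chooses; possibly out of state (11.4, 25.6) | May not |
| Stage 2 follow-up by Zoom, for women who cannot come in (Short-term Follow-up) | Not stated; not at the lab | May not |
| Exit interview by phone after 12 weeks (section 10.3) | Not stated | May not |

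**Step 1: is there another staff step?** In sections 13.3, 18.1 to 18.8 and 20.1 to 20.2, I find no instruction for staff to contact 911, local police or a crisis line. Nor is anyone told to ask where the woman is. The SAP does not address emergencies.

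**Step 2: does the pathway cover remote triggers?** Yes for online assessments, which 20.2 names. Zoom and phone interviews are assigned to neither the online nor the in-person branch. The trigger covers any evidence, however, and the backup sentence is not limited to one mode, so the same backup is the only one on offer.

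**Step 3: does the referral material fill the gap?** Only in part.
- The list attached to surveys depends on the woman using it herself.
- The interviewers' link is available to staff, but it is tied to distress noticed in an interview. It is not a step for immediate danger, and it does not cover a trigger that arises in an online survey.

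**Step 4: who calls if the clinician is unreachable?** For an online trigger, the clinician is the only person told to phone the woman. If the clinician cannot be found, 20.2 says which service to contact, but not who speaks with the woman or finds out where she is.

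**Step 5: can the size be counted?** No. That would need a rate of emergency triggers, a rate of unreachable clinicians and the share of women off campus. The documents give none of these.

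**The case against.** Four points on the other side deserve weight.

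- **The harm is inferred.** No section says how far the PSC or Campus Security can act. The text says only that they are contacted, and either might phone the woman or pass the case to local police. A reader might infer that they cannot reach a woman off campus. The documents do not support that; they support only that these services may be unable to.
- **Live danger is unlikely to surface in a survey.** Under section 10.3, bi-weekly reports look back over social occasions since the last assessment. Most remote triggers would be distress or a past assault, where a conversation matters more than physical reach. This stands and lowers the expected frequency. It does not remove the gap, since a report of past events can reveal a continuing threat, and the Zoom and phone interviews are live.
- **Staff have other resources.** Interviewers have the link to referral resources, so it would be wrong to infer that women at other colleges have no route to outside help. Nor do the documents say that the PSC or the Counseling Center would turn those women away. They are silent on the matter.
- **A fuller staff script may exist.** Sections 18.1 and 20.2 refer to an emergency protocol and an interviewer protocol, and staff might call 911 on their own initiative. It cannot be concluded that they would not. But 18.1 points to the text of 20.2 for the description, and that text gives a specific rule without this step.

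**Conclusion.** The point holds in limited form. For remotely identified emergencies, section 20.2 states a specific backup that fits poorly with where the women may be, and it allows up to an hour to pass before that backup is used. For women on the UB campus the rule is adequate.

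No number of women can be attached to this. A reader might take the expected victimization rate of about 30% over 3 months (section 16.1) as its size. With 24 + 24 = 48 dyads, or 96 women, that gives 0.30 × 96 = 28.8; with the 88 women in section 16.2 it gives 0.30 × 88 = 26.4. Those are expected reports of any victimization, on a definition that runs from unwanted attention to completed rape (section 10.3). They are not emergencies, still less emergencies off campus with the clinician out of reach. They show only that a trigger is foreseeable.

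The conclusion rests on two assumptions: that the campus services' reach is limited away from UB, and that no separate staff script already supplies the missing step. The situation requires several things to coincide and should be uncommon, but the possible consequence is serious and the remedy is small. Low-to-moderate priority, medium confidence. The planned analyses are not affected.

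**What to change.** Amend section 20.2 for triggers identified remotely:

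1. The staff member who identifies or responds to the trigger asks the woman where she is now. For an online trigger with the clinician unreachable, the text should say which staff member phones her.
2. If danger appears immediate and she is not on the UB campus, staff contact 911 or local emergency services where she is. They do so without waiting the hour for the clinician, and tell her first where possible. The campus should be named as UB, so that a woman on another college's campus is not routed to UB Campus Security.
3. If danger is not immediate and the clinician cannot be reached, the staff member offers a national crisis line or a provider from the existing local and national referral list (section 13.3).

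Keep the PSC and Campus Security for women on the UB campus.

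The cost is a few sentences of protocol wording and one location question in the emergency script. There may also be a small effect on candour if women know that outside services could be called. Limiting outside contact to immediate danger contains that effect and respects the balance in section 18.2 between safety and truthful reporting.
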